7.7.8.2 Procedures for Eliciting and Recording Adverse Events

Eliciting Adverse Events

An open-ended or non-directed method of questioning should be used at each study visit to elicit the reporting of AEs.

Recording Adverse Events

The following information should be recorded on the Adverse Events and Pre-existing Conditions CRF:

- Description including onset and resolution dates
- Whether it met SAE criteria
- Severity
- Relationship to study treatment or other causality
- Outcome

Diagnosis vs. Signs or Symptoms

In general, the use of a unifying diagnosis is preferred to the listing out of individual symptoms. Grouping of symptoms into a diagnosis should only be done if each component sign and/or symptom is a medically confirmed component of a diagnosis as evidenced by standard medical textbooks. If any aspect of a sign or symptom does not fit into a classic pattern of the diagnosis, report the individual symptom as a separate adverse event.

Important exceptions for this study are adverse reactions associated with the infusion of study drug. For IRRs, do not use the NCI CTCAE terms of “cytokine release syndrome,”

“acute infusion reaction,” or “allergic or hypersensitivity reaction.” Instead, record each sign or symptom as an individual AE. If multiple signs or symptoms occur with a given infusion-related event, each sign or symptom should be recorded separately with its level of severity.

Recording Serious Adverse Events

For SAEs, record the event(s) on both the CRF and an SAE form.

The following should be considered when recording SAEs:

- Death is an outcome of an event. The event that resulted in the death should be recorded and reported on both an SAE form and CRF.
- For hospitalizations, surgical, or diagnostic procedures, the illness leading to the surgical or diagnostic procedure should be recorded as the SAE, not the procedure itself. The procedure should be captured in the narrative as part of the action taken in response to the illness.

Progression of the Underlying Malignancy

Since progression of underlying malignancy is being assessed as an efficacy variable, it should not be reported as an AE or SAE. The terms “Disease Progression”, “Progression of Disease” or “Malignant Disease Progression” and other similar terms should not be used to describe an AE or SAE. However, clinical symptoms of progression may be reported as AEs or SAEs if the symptom cannot be determined as exclusively due to progression of the underlying malignancy or does not fit the expected pattern of progression for the disease under study. In addition, complications from progression of the underlying malignancy should be reported as AEs or SAEs.

Pregnancy

Notification to Drug Safety

Complete a Pregnancy Report Form for all pregnancies that occur from the time of first study drug dose until 6 months after the last dose of study drug(s). Email or fax to the sponsor’s Drug Safety Department within 48 hours of becoming aware of a pregnancy. All pregnancies will be monitored for the full duration; all perinatal and neonatal outcomes should be reported. Infants should be followed for a minimum of 8 weeks.

Collection of data on the CRF

All pregnancies (as described above) that occur within 30 days of the last dose of study drug(s) will also be recorded on the Adverse Events and Pre-Existing Conditions CRF.

Abortion, whether accidental, therapeutic, or spontaneous, should be reported as an SAE. Congenital anomalies or birth defects, as defined by the ‘serious’ criterion above (see definitions Section [7.7.8.1](#)) should be reported as SAEs.

Potential Drug-Induced Liver Injury

The observation of the critical importance of altered liver function has been referred to informally as Hy's Law (Reuben 2004). Hy's Law can be used to estimate severity and the likelihood that a study drug may cause an increased incidence of severe hepatotoxicity.

The absence of hepatotoxicity in clinical trials provides a limited predictive value for potential hepatotoxicity in the clinical setting(s) being studied. However, finding 1 Hy's Law case in clinical trials is ominous; finding 2 cases is highly predictive of a potential for severe drug-induced liver injury (DILI).

Definition

Briefly, potential Hy's Law cases include the following 3 components:

1. Aminotransferase (ALT and/or AST) elevation $>3 \times$ ULN

AND

2. Total bilirubin $>2 \times$ ULN, without initial findings of cholestasis (i.e., elevated serum alkaline phosphatase),

AND

3. No other immediately apparent possible causes of aminotransferase elevation and hyperbilirubinemia, including, but not limited to, viral hepatitis, pre-existing chronic or acute liver disease, or the administration of other drug(s) known to be hepatotoxic.

Reporting Requirements

Any potential Hy's Law case should be handled as a suspected unexpected serious adverse reaction (SUSAR) associated with the use of the drug and reported promptly to the sponsor.

Reporting should include all available information and should initiate close follow-up until complete resolution of the problem and completion of all attempts to obtain supplementary data.

Follow-up for Abnormal Laboratory Results Suggesting Potential DILI

In general, an increase of serum ALT or AST to $>3 \times$ ULN should be followed by repeat testing within 48 to 72 hours of serum ALT, AST, alkaline phosphatase, and total bilirubin, to confirm the abnormalities and to determine whether they are worsening.

Appropriate medical assessment should be initiated to investigate potential confounding factors and alternative causes of hepatotoxicity.

7.7.8.3 Reporting Periods for Adverse Events, Serious Adverse Events, and Adverse Events of Special Interest

The safety reporting period for all AEs and SAEs is from study Day 1 (predose) through the EOT visit or 30 days after the last study treatment (tisotumab vedotin), whichever is later.

However, all study protocol-related AEs are to be recorded from the time of informed consent. All SAEs that occur after the safety reporting period and are considered study treatment-related in the opinion of the investigator should also be reported to the sponsor.

SAEs will be followed until significant changes return to baseline, the event stabilizes (recovering/resolving) or is no longer considered clinically significant by the investigator, or the patient dies or withdraws consent. All non-serious AEs will be followed through the safety reporting period. Certain non-serious AEs of interest (i.e., all ocular events) will be followed until resolution, return to baseline, or study closure.

7.7.8.4 Serious Adverse Events and AESIs Requiring Immediate Reporting

Within 24 hours of observing or learning of any SAE, investigators are to report the event to the sponsor, regardless of the relationship of the event to the study treatment regimen. Additionally, all ocular AEs (any grade, whether they meet seriousness criteria or not) must be reported to the sponsor within 24 hours. Ocular AEs are the only non-serious events that should be reported on an SAE form.

For initial SAE reports, available case details are to be recorded on an SAE form. At a minimum, the following should be included:

- Patient number
- Date of event onset
- Description of the event
- Study treatment, if known

The completed SAE form and SAE Fax Cover Sheet are to be emailed or faxed to the sponsor's Drug Safety Department within 24 hours (see email or fax number specified on the SAE report form) unless otherwise instructed on the sponsor's SAE form.

Relevant follow-up information is to be submitted to the sponsor as soon as it becomes available.

7.7.8.5 Sponsor Safety Reporting to Regulatory Authorities

Investigators are required to report all SAEs, including anticipated SAEs, to the sponsor (see Section 7.7.8.4). Investigators must also report all ocular AEs, whether or not they meet seriousness criteria, to the sponsor.

The sponsor will report all SAEs and ocular AEs to regulatory authorities as required per local regulatory reporting requirements. In the United States, endpoints that assess disease-related mortality or major morbidity, as well as other SAEs that are not study endpoints but are known consequences of the underlying disease or condition that are anticipated to occur in the study population, should not be reported to the FDA as individual IND safety reports per the final rule amending the IND safety reporting requirements under 21 CFR 312.32 and the FDA's guidance Safety Assessment for IND Safety Reporting Guidance for Industry (draft guidance December 2015).

In this study, progression of underlying malignancy is not reported as an AE or SAE. No individual IND safety reports will be submitted for progression of underlying malignancy. Progression of underlying malignancy will be evaluated as an efficacy endpoint.

7.8 Appropriate ness of Measurements

The safety measures that will be used in this trial are considered standard procedures for evaluating the potential adverse effects of study medications.

Response will be assessed according to RECIST v1.1, which are standardized criteria for evaluating response in the solid tumors comprising the cohorts in this study. The intervals of evaluation in this protocol are considered appropriate for disease management.

Immunogenicity is commonly assessed for biologics; therefore, standard tests will be performed to detect the possible presence of specific antibodies to tisotumab vedotin. Pharmacokinetic assessments are also common in clinical studies to help characterize dose-exposure-response relationships.

8 DATA QUALITY CONTROL AND QUALITY ASSURANCE

8.1 Site Training and Monitoring Procedures

A study manual with instructions for study compliance and CRF completion will be provided. Prior to the enrollment of patients at the site, Seattle Genetics or its designated clinical and medical personnel will review the following items with the investigator and clinic staff:

- The protocol, study objectives, eligibility requirements, study procedures, registration, and withdrawal processes
- Current Investigator's Brochure
- Recording and reporting AEs and SAEs
- Enrollment goals and study timelines
- The CRF completion process and source documentation requirements
- Monitoring requirements
- IRB/IEC review and approval process
- Informed consent process
- Good Clinical Practice guidelines and related regulatory documentation requirements
- Key study team roles and responsibilities
- Investigational product storage, accountability, labeling, dispensing, and record keeping
- Patient coding
- Study samples/specimen collection, handling and shipping
- Protocol compliance
- Clinical study record keeping, document retention, and administrative requirements

Monitoring visits will occur periodically, with frequency dependent on the rate of enrollment and workload at each site. During monitoring visits, the Seattle Genetics representative will typically review regulatory documentation, CRFs, source documentation, and investigational product storage, preparation, and accountability. The CRFs will be reviewed for completeness, adherence to the provided guidelines, and accuracy compared to the source documents. The investigators must ensure that the monitor is allowed to inspect all source documents pertinent to study patients, and must cooperate with the monitor to ensure that any problems noted in the course of the trial are resolved. The investigator must maintain a comprehensive and centralized filing system of all study-related documentation that is suitable for inspection by Seattle Genetics or its designated monitors and by quality assurance auditors, or representatives of regulatory authorities.

8.2 Data Management Procedures

Seattle Genetics will provide CRF Completion Guidelines for eCRF data entry. Study specific data management procedures will be maintained in the data management plan. Queries resulting from edit checks and/or data verification procedures will be posted electronically in the eCRF.

8.3 Access to Source Data

The investigator will permit the sponsor's representatives to monitor the study as frequently as the sponsor deems necessary to determine that protocol adherence and data recording are satisfactory. Appropriate measures to protect patient confidentiality are to be employed during monitoring. The CRFs and related source documents will typically be reviewed in detail by the monitor at each site visit. Original source documents or certified copies are needed for review. This review includes inspection of data acquired as a requirement for participation in this study and other medical records as required to confirm that the information contained in the CRFs, such as disease assessments, AEs, and concomitant medications, is complete and correct. Other study records, such as correspondence with the sponsor and the IRB/IEC and screening and drug accountability logs will also be inspected. All source data and study records must also be available for inspection by representatives of regulatory authorities and the IRB/IEC.

8.4 Accuracy and Reliability of Data

Steps to be taken to assure the accuracy and reliability of data include:

- The selection of qualified investigators and appropriate study centers.
- Review of protocol procedures with the investigators and associated personnel prior to the study.
- Periodic monitoring visits by the designated monitor(s).
- CRFs will be reviewed for accuracy and completeness by the designated monitor(s) during monitoring visits to the study centers and/or by centralized monitoring. Any discrepancies will be resolved with the investigator or designees as appropriate.

8.5 Quality Assurance Procedures

The Research and Development Quality group or its designee may conduct audits at the clinical site or other study-related facilities and organizations. Audit reports will be retained by the Research and Development Quality group of Seattle Genetics as part of the written record.

8.6 Data Handling and Record Keeping

8.6.1 Data Handling

It is the investigator's responsibility to ensure the accuracy, completeness, legibility, and timeliness of the data reported to the sponsor in the CRFs and in all required reports. Data reported on the CRF that is derived from source documents should be consistent with the source documents or the discrepancies should be explained.

Any change or correction to a CRF will be maintained in an audit trail within the electronic data capture system. Data changes may only be made by those individuals so authorized. The investigator should retain records of the changes and corrections, written and/or electronic.

8.6.2 Investigator Record Retention

The investigator shall retain study drug disposition records and all source documentation (such as original ECG tracings, laboratory reports, inpatient or office patient records) for the maximum period required by the country and institution in which the study will be conducted, or for the period specified by Seattle Genetics, whichever is longer. The investigator must contact Seattle Genetics prior to destroying any records associated with the study. If the investigator withdraws from the study (due to relocation, retirement, etc.), the records shall be transferred to a mutually agreed upon designee, such as another investigator or IRB/IEC. Notice of such transfer will be provided in writing to Seattle Genetics.

9 DATA ANALYSIS METHODS

9.1 Determination of Sample Size

Up to approximately 222 patients may be enrolled in the study. This includes approximately 6–12 patients in the safety run-in phase, approximately 30 patients in each of 2 randomized Part A cohorts, and the possible expansion of an additional 70 patients in one of the 2 Part A cohorts. Part B will enroll approximately 80 patients including approximately 60 patients who have received 1 to 3 prior lines of therapy, including bevacizumab treatment.

Analysis regarding expansion of Part A will be conducted when approximately 30 patients per cohort have at least one post-baseline response assessment per RECIST v1.1 or have discontinued from the study or started subsequent cancer therapy.

A cohort may be expanded to further characterize antitumor activity if the safety profile is acceptable, other efficacy endpoints are comparable to current standard of care, and the number of confirmed CR or PR meet cohort-specific criteria.

The sample size is not based on power calculations for formal hypothesis testing, but is selected based on ORR estimate precision as characterized by 95% confidence intervals (CIs). For a sample size of 30 patients (Part A) and 60 patients (Part B with 1 to 3 prior lines of therapy, including bevacizumab treatment) per cohort (or 100 patients, if a treatment arm from Part A is expanded), assuming the confirmed ORR is between 20% and 40%, the 2-sided 95% exact CIs are summarized below.

Confirmed ORR	95% Exact CI (N=30)	95% Exact CI (N=60)	95% Exact CI (N=100)
15%	(4%, 31%)	(7%, 27%)	(9%, 24%)
20%	(8%, 39%)	(11%, 32%)	(13%, 29%)
30%	(15%, 49%)	(19%, 43%)	(21%, 40%)
40%	(23%, 59%)	(28%, 53%)	(30%, 50%)

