Interim futility analysis will be performed on Part B after at least 20 patients with 1 to 3 prior lines of therapy, including bevacizumab treatment, have been treated and had at least one response assessment post-baseline. The Bayesian predictive probability approach will be used to determine the futility criteria ([Lee 2008](#)). At the time of the interim futility analysis, the predictive probability of success (PPoS) will be calculated. Based on activity and safety data, together with the PPoS, the cohort may continue or be stopped early by the sponsor. While the interim futility analysis is performed, enrollment in Part B may continue. A cohort may also be discontinued at any point at the discretion of the sponsor.

On a periodic basis, a Safety Monitoring Committee (SMC) will monitor the safety of patients participating in the trial. The SMC will be responsible for evaluating the results of safety analyses and will make recommendations to the sponsor. Ongoing, real-time review of patient safety and serious adverse events (SAEs) will also be conducted by the sponsor's Drug Safety department throughout the study.

During the safety run-in period, the SMC will assess tolerability and safety of tisotumab vedotin (refer to SMC charter for additional details) at the end of the DLT period for each dose level. Ad hoc meetings of the SMC may be convened prior to the safety evaluation period if safety data indicate.

An individual's dose may be modified based upon treatment-related AEs. Response will be assessed every 6 weeks for the first 6 months, every 12 weeks for the next 6 months, and then every 6 months after that. RECIST v1.1 will be used by the investigator to score responses for primary and secondary endpoints as well as progression. Objective responses will be confirmed with repeat scans at least 4 weeks after the first documentation of response. The study will be closed 3 years after the last patient is enrolled or when no patients remain in long-term follow-up, whichever comes first. Additionally, the sponsor may terminate the study at any time.

Figure 2: Study design

Safety run-in will start with 3Q4W dosing of 0.9 tisotumab vedotin in approximately 12 patients. If deemed safe, this dose will escalate to 1.2 mg/kg. If not deemed safe, it will de-escalate to 0.65 mg/kg. Part B will enroll only after the 0.9 mg/kg 3Q4W dose is deemed safe by the SMC.

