6.5 Response Assessments

Time points for radiographic exams should be calendar-based and do not depend on cycle visits. Imaging should be conducted on the following schedule until disease progression, start of a new cancer therapy, consent withdrawal, study termination by the sponsor, or death, whichever comes first:

- Every 6 weeks (\pm 7 days) for 6 months after the first dose of tisotumab vedotin
- Every 12 weeks (\pm 7 days) for the next 6 months (i.e., until 1 year after first dose)
- Every 6 months (\pm 2 weeks) thereafter

Blood collections for CA-125 status should correspond as closely as possible with imaging visits (\pm 5 days).

Responses must be evaluated with a confirmatory scan at least 4 weeks after initial response.

6.6 End of Treatment Visit (30 to 37 days after last dose of study drug)

End of Treatment (EOT) visits should occur 30 to 37 days after the last dose of study drug unless delayed due to an AE. Note: The time to EOT visit may be longer than 37 days.

However, EOT evaluations must be performed before initiation of a new (non-protocol) therapy. If EOT evaluations are completed before 30 days after the last study treatment, the patient will be contacted 30 to 37 days following the last treatment to assess for adverse events.

- Physical examination
- Vital signs
- Chemistry panel (results to be submitted to central laboratory)
- CBC with differential (results to be submitted to central laboratory)
- Pregnancy test for patients of childbearing potential
- Coagulation parameters (fibrinogen, INR, PT, and aPTT) (results to be submitted to central laboratory)
- HgbA1c (results to be submitted to central laboratory)

- Blood collection for CA-125 (results to be submitted to central laboratory; not required if conducted within 4 weeks prior to EOT)
- Eye exam performed by investigator
- ECOG performance status
- ECG
- Imaging (not required if conducted within 4 weeks prior to EOT)
- Subsequent anti-cancer therapy status
- Survival status
- Blood sample for PK evaluation
- Blood sample for ATA evaluation
- Blood sample for plasma proteomic analysis
- Blood sample for plasma mutational analysis
- Blood sample for plasma exosome analysis
- Blood sample for PBMC immune subsets analysis
- Parts A and B, US patients only: patient-reported outcomes questionnaires (both instruments)

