9.2 Study Endpoint Definitions

9.2.1 Confirmed ORR

Confirmed ORR is defined as the proportion of patients who achieve a confirmed CR or PR according to RECIST v1.1 as assessed by the investigator. Patients who do not have at least 2 post-baseline response assessments (initial response and confirmation scan) will be counted as non-responders.

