9.3.9 Interim Analyses

A safety analysis will be conducted at end of DLT period for each dose level in the safety run-in portion to evaluate the tolerability of dose-dense regimen. A SMC consisting of the investigators, study medical monitor, biostatistician, and drug safety representative will review the data before proceeding to Part A.

Interim analysis for futility will be performed on Part B after at least 20 patients with 1 to 3 prior lines of therapy, including bevacizumab treatment, have been treated and had at least one response assessment post-baseline.

The Bayesian predictive probability approach will be used to determine the futility criteria (Lee 2008). At the time of the interim futility analysis, the PPoS will be calculated. PPoS is the probability of achieving “success” should the cohort be continued to the maximum sample size of 60 in the target population (1 to 3 prior lines of therapy, including bevacizumab treatment) given the data observed at interim, and the cohort is considered “success” if the posterior probability that the ORR exceeds the response rate of current standard of care (i.e., 12% as reference in Section 3.2) is greater than 70%.

Both the confirmed and unconfirmed CR or PR observed at interim will be counted as a response for the calculation of PPoS. It is appropriate to include the unconfirmed response for the purpose of interim analysis because based on the estimates from GEN701 trial, about 60% of the responders will respond at their first post-baseline scan and approximately 75% of the confirmed/unconfirmed responses will eventually be confirmed. Table 9 summarizes the PPoS based on the number of responses observed among the first 20 patients. Details of the calculation of PPoS are shown in Appendix I.

Table 9: PPoS based on responses among the first 20 patients pretreated with bevacizumab

No. of responses* among the first 20 patients	PPoS
	PROC bevacizumab pretreated ($p_0=12\%$)
0	<1%
1	4%
2	20%
3	49%
4	77%
5	93%
6	99%
7	>99%
8	>99%
9	>99%
10+	>99%

* P_0 is the response rate of current standard of care of each cohort

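### The Part A expansion analysis can run after one post-baseline scan per patient but is judged on confirmed responses, so recently enrolled responders are counted as failures in both arms

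*Protocol*

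**What the plan says.** Protocol 9.1 sets the timing: "Analysis regarding expansion of Part A will be conducted when approximately 30 patients per cohort have at least one post-baseline response assessment", "or have discontinued from the study or started subsequent cancer therapy". The next paragraph makes expansion depend on acceptable safety, on other efficacy endpoints, and on whether "the number of confirmed CR or PR meet cohort-specific criteria". No number is given for those criteria. The synopsis, protocol 3.1 and SAP 4 repeat the timing; SAP 6.2 repeats both timing and criterion.

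On confirmation, protocol 6.5 says "Responses must be evaluated with a confirmatory scan at least 4 weeks after initial response", and 9.2.1 says "Patients who do not have at least 2 post-baseline response assessments (initial response and confirmation scan) will be counted as non-responders". SAP 6.4.2 and 7.5.1.1 keep the 4-week minimum. Protocol 3.1 gives the scan interval: "Response will be assessed every 6 weeks for the first 6 months".

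The Part B futility analysis in protocol 9.3.9 (SAP 8) also needs only one post-baseline assessment. There the plan counts confirmed and unconfirmed responses together and explains why: "It is appropriate to include the unconfirmed response for the purpose of interim analysis". Its reasons are that about 60% of responders in GEN701 respond at the first scan and about 75% of responses are eventually confirmed. Part A has no such provision. SAP 6.10 and SAP 8 do not mention the expansion analysis.

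**The concern.** A patient can satisfy the timing rule with a single Week 6 scan, but one scan cannot yield a confirmed response. A Week 6 response is confirmed at Week 10 at the earliest, or Week 12 on the routine schedule. A Week 12 response is confirmed at Week 16 to 18. A patient who has already left the study is final at the trigger, whereas a recently enrolled responder is still scored as a failure. The shortfall is set by how fast patients enrolled, not by how active the drug is.

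The decision at stake is whether up to 70 more patients are treated in one Part A arm. It is the only efficacy decision point stated for Part A, and neither a threshold nor operating characteristics are given for it.

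**Working it through.** **The plan's own figure.** The only precision figures for Part A are the exact intervals in 9.1. For 6 of 30 (20%), the Clopper-Pearson limits are 7.7% and 38.6%, which round to the stated (8%, 39%). That table describes mature data and says nothing about the count at the trigger.

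**Inputs from the documents.**
- 30 patients per arm (9.1).
- Scans every 6 weeks (3.1).
- Confirmation at least 4 weeks after first response (6.5).
- 60% of responders first seen at the first scan (9.3.9). That figure covers confirmed and unconfirmed responders in GEN701; using it for confirmed responders is an assumption.

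**Assumptions.**
- Uniform accrual over A weeks, with the trigger when the last patient reaches Week 6.
- The remaining 40% of confirmed responders first seen at Week 12 (30%) and Week 18 (10%).
- Confirmation c = 4 or 6 weeks after first response.
- Months converted at 30.4375 days (SAP 6.4.1), so 3, 6, 9 and 12 months are A = 13.04, 26.09, 39.13 and 52.18 weeks.

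**Who cannot yet be confirmed.** With 30 patients evenly spaced and the last at Week 6, the number with under 10 / under 12 weeks of follow-up is 9 / 14 (13 weeks of accrual), 5 / 7 (26 weeks) and 3 / 4 (52 weeks).

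**Visible share.** Follow-up at the trigger is uniform between 6 and 6 + A weeks. A response first seen at Week t is confirmed by then with probability (A + 6 − t − c)/A, floored at 0. The share is

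S = 0.6(A − c)/A + 0.3(A − 6 − c)/A + 0.1(A − 12 − c)/A, each term floored at 0.

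For 3 months and c = 4: 0.6 × 0.693 + 0.3 × 0.233 + 0 = 0.486. For c = 6: 0.6 × 0.540 + 0.3 × 0.080 + 0 = 0.348.

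**Effect on the count.** The number visible is Binomial(30, ORR × S). The plan states no threshold, so 3 or fewer of 30 is used as an illustrative failing result. Ranges cover c = 4 and c = 6.

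| Accrual | Share S | Expected count, true ORR 20% (mature: 6) | P(≤3 of 30), true ORR 20% | P(≤3 of 30), true ORR 30% |
|---|---|---|---|---|
| Mature data | 100% | 6.0 | 12.3% | 0.9% |
| 3 months | 34.8–48.6% | 2.1–2.9 | 66.7–84.7% | 34.5–61.6% |
| 6 months | 65.5–73.2% | 3.9–4.4 | 34.2–43.4% | 7.9–13.2% |
| 9 months | 77.0–82.1% | 4.6–4.9 | 25.1–30.0% | 4.1–6.0% |
| 12 months | 82.7–86.6% | 5.0–5.2 | 21.2–24.5% | 2.9–3.9% |

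**After the fix.** If the analysis waits for Week 12 scans and for confirmation of anything seen there, minimum follow-up is up to 16 weeks (c = 4) or 18 weeks (c = 6). Only Week 18 responders can then be missing, and S = 0.9 + 0.1(A − 6)/A. This is 95% for 3 months (0.9 + 0.1 × 7.04/13.04) and 99% for 12 months (0.9 + 0.1 × 46.18/52.18).

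**Counting unconfirmed responses at the early trigger.** Setting c = 0 gives the share of responses already seen: 0.770 at 3 months and 0.942 at 12 months. If only 75% of responses confirm, the all-response count is 0.770/0.75 = 1.03 to 0.942/0.75 = 1.26 times the eventual confirmed count. In the ovarian data in protocol 1.3.3.2, 3 of 6 (GEN701) and 2 of 4 (GEN702) responses were confirmed. At that 50% rate the ratio is 1.5 to 1.9.

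**The case against.** The strongest reply is that one assessment is a floor. Patients who enrolled earlier will have several scans at the trigger, so a reader who infers that almost no confirmed responses could be seen goes too far. That stands, and the calculation allows for it: the shortfall comes only from recent enrollees.

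A reader might also infer that the choice between arms is biased. The documents do not support that. Patients are randomized 1:1 and concurrently, and protocol 6.5 says "Time points for radiographic exams should be calendar-based and do not depend on cycle visits", so the expected under-count is similar in both arms. The comparison becomes noisier, not tilted.

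Nor do the documents support quoting the 3-month probabilities as the expected effect. They would need 60 patients randomized in three months, and no accrual rate is given. The cut-off of 3 or fewer is likewise illustrative. The unpublished criteria may have been set for immature data, in which case the bias would be smaller or absent, but neither document says so.

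Finally, expansion is discretionary and also depends on safety and other endpoints, and a stricter count may be defensible for a decision to add patients than for a futility stop. Both points limit the consequence. Neither explains why a criterion that needs two scans is applied at a time defined by one.

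**Conclusion.** The mismatch is real, appears in both documents and is not resolved elsewhere. Applied as written, the rule under-counts confirmed responses in both arms against any absolute threshold meant for mature data. Under the stated timing assumptions, about 13–17% of eventual confirmed responses are missing with 12 months of accrual and about 27–35% with 6 months. With the illustrative gate and a true ORR of 20%, the chance of an apparently inactive arm rises from 12% to about 21–25% (12 months) or 34–43% (6 months). At a true ORR of 30% it rises from 1% to 3–4% or 8–13%.

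A reader might go on to infer that the reported ORR is compromised or that an active regimen would necessarily be dropped. Neither follows. The primary analysis waits for 6 months of follow-up (protocol 9.3.1.9), and the count is one of several inputs to a discretionary decision. The mismatch itself is certain; its size is not, because accrual, the timing of later responses and the threshold are not in the documents.

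**What to change.** In the synopsis, protocol 3.1 and 9.1, and SAP 4 and 6.2, redefine the trigger. The analysis runs when about 30 patients per arm have had the opportunity for at least two post-baseline assessments and any response seen by then has had its confirmatory scan, or the patient has progressed, died, discontinued or started other therapy. The cost is a delay in the expansion decision of about 6 weeks, if nothing new is seen at Week 12, to about 12 weeks, if a Week 12 response has to be confirmed at Week 18. No patients or procedures are added.

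If the early trigger is kept, count confirmed plus not-yet-confirmed responses, following the Part B approach, and write down the threshold, adjusted for the expected confirmation rate (75% in 9.3.9, 50% in the ovarian data in 1.3.3.2). Without that adjustment, the change would replace an under-count with an over-count. Dropping responses that have already failed to confirm would reduce the over-count but not remove it. The cost is that some counted responses will not confirm.
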